Study Endpoints	
Primary endpoints:
 
1. DLTs, classified and graded according to the National Cancer Institute's Common Terminology Criteria for Adverse Events (NCI CTCAE, version 5.0).2. Frequency of treatment-emergent adverse events (TEAEs), and serious adverse events (SAEs) related to APR-246 in combination with venetoclax and/or azacitidine during the trial.3. The RP2D of APR-246 (the dose at which <2 out of 6 patients experience dose-limiting toxicity during the safety assessment period). 
Secondary endpoints:
 
1. CR rate, defined as the proportion of patients who achieve CR.2. CR + CRI rate, defined as the proportion of patients who achieve CR or CRI.3. CR + CRh rate, defined as the proportion of patients who achieve CR or CRh.4. Overall response rate (ORR), defined as the proportion of patients achieving CR, complete remission with incomplete hematologic recovery (CRI), complete remission with incomplete platelet recovery (CRp), partial remission (PR) and morphologic leukemia-free state (MLFS) by the IWG 2003 criteria (APPENDIX I). The complete remission with partial hematologic recovery (CRh) rate will also be determined and is defined as bone marrow blasts <5%, ANC >0.5 × 10⁹/L and platelets >50 × 10⁹/L.5. Overall survival (OS), measured from the date of initiating study treatment to the date of death. Patients who have not died by the analysis data cut-off date will be censored at their last date of contact.6. Rate of red blood cell (RBC) and/or platelet transfusion independence (TI) for at least 56 days.7. Progression-free survival (PFS), defined from the date of initiating study treatment to the date of disease progression or death as a result of any cause.8. Proportion of patients who transition to HSCT.9. Pharmacokinetic parameters: maximum concentration (C_{max}), area under curve (AUC), V_d and clearance (CL) of APR-246 and time of maximum concentration (T_{max}), C_{max} and AUC of venetoclax.

	
Exploratory endpoints:
 
1. Exploratory molecular analyses may include, but are not limited to: TP53 VAF by NGS, p53 immunohistochemistry (IHC), mutations in other genes by NGS, RNA expression.

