--	--

	
any cause, whichever occurs first. Patients alive with no progressive disease will have their DOR censored at the date of the last clinical assessment. The duration of CR will be summarized in each treatment arm by providing duration of complete response (DOCR) and duration of overall response (DOR), using Kaplan-Meier methodology. DoR endpoints will not be formally compared between treatment arms.
 
Overall response will be summarized in number (%) of patients in each category of responses and ORR will be analyzed by using the similar method as CR rate.
 
Survival data are collected at treatment and follow-up periods. Patients will be followed until death or withdrawal of consent for study participation. Overall survival (OS) is defined as the number of days from the first day of treatment to the date of death. Kaplan-Meier methodology will be utilized.
 
Progression-free survival (PFS) is defined as the time from the first day of treatment to disease progression or death from AML, whichever occurs first. If neither event occurs, PFS will be censored at the date of the last clinical assessment. Kaplan-Meier methodology will be utilized.
 
Safety Analyses
 
Safety data including AEs, vital signs, laboratory data, electrocardiogram (ECG), physical exam will be tabulated for the safety population. AEs will be tabulated by System Organ Class (SOC), preferred term, severity, and relationship to treatments. The tabulation of laboratory parameters will include the normal ranges for each parameter. Each value will be classified as falling above, below, or within the normal range. Laboratory parameters will also be tabulated by maximum NCI CTCAE v5.0 severity grade.
 
Pharmacokinetic Analysis
 
PK sampling for APR-246 are performed in Cycle 1, on Days 1, 2 and 4, and on Day 4 of every subsequent cycle.
 
PK sampling for venetoclax is performed on Days 1, 2, 22 and 23 of Cycle 1 and on Day 4 of Cycles 2 – 5.
 
Non-compartmental or population pharmacokinetic methods will be used to derive APR-246 and venetoclax PK parameters (C_{max}, T_{max}, AUC, V_d and CL).
 
The pharmacokinetics of APR-246 and venetoclax will be summarized using descriptive statistics (mean, standard deviation, CV% mean, geometric mean, CV% geometric mean) and compared with historical control data.
 
APR-246 AUC and C_{max} will then be tested for association with signs of efficacy and safety. If an observable trend exists, a PK/PD model will be developed to evaluate the exposure-response relationship between APR-246 plasma exposure and outcome measures in the presence of venetoclax. Demographic and clinical data (ethnicity, current age, body weight, sex, disease status, etc.) will be utilized to assess interpatient variability in the PK and PK/PD relationships.

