8.3 Progression-Free Survival (PFS)

Progression-free survival (PFS) is defined for each patient as the time from start of treatment to the date of the first documented progression or death due to any cause. Patients who die without a reported prior progression will be considered to have progressed on the date of their death. Patients who did not progress or die will be censored on the date of their last evaluable tumor assessment. Patients who started any subsequent therapy without a prior reported progression will be censored at the last evaluable tumor assessment prior to the initiation of the subsequent anticancer therapy.

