9.5 Efficacy

CR will be summarized for all enrolled patients as the proportion of patients (%) with CR. In addition to presenting the CR rate, its associated exact 95% CI for each treatment arm will also be presented. CR rate will not be formally compared between treatment arms.

DoR will be defined as the time from the date when criteria for response are met to the date of PD or death due to any cause, whichever occurs first. Patients that are alive without relapse or progression will have their DOR censored at the date of the last clinical assessment. The duration of CR will be summarized in each treatment arm by providing DOCR and DOR, using Kaplan-Meier methodology. DoR endpoints will not be formally compared between treatment arms.

Overall response will be summarized in number (%) of patients in each category of responses and ORR will be analyzed by using the similar method as CR rate.

Survival data will be collected at treatment and follow-up periods. Patients will be followed until death, or withdrawal of consent for study participation. OS is defined as the number of days from the date of enrollment to the date of death. Kaplan-Meier methodology will be utilized.

PFS will be defined as the time from the date of enrollment to disease progression or death from AML whichever occurs first. If neither event occurs, PFS will be censored at the date of the last assessment. Kaplan-Meier methodology will be utilized.

Transition rate to SCT will be analyzed using the similar methods as CR.

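### PFS is defined inconsistently: section 9.5 and the synopsis analysis count only AML deaths, 9.5 alone starts at enrollment, and 8.3 alone censors at subsequent therapy

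*Combined protocol and SAP*

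**What the plan says.** PFS is defined in five places in the protocol.

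- **Synopsis, Study Endpoints:** "defined from the date of initiating study treatment to the date of disease progression or death as a result of any cause".
- **Section 9.3.2:** the same start and the same any-cause death component, with progression judged by the IWG 2003 criteria.
- **Section 8.3:** from start of treatment to "the date of the first documented progression or death due to any cause". It adds: "Patients who die without a reported prior progression will be considered to have progressed on the date of their death". It also has a rule found nowhere else: "Patients who started any subsequent therapy without a prior reported progression will be censored at the last evaluable tumor assessment" before that therapy began.
- **Synopsis, Efficacy Analyses:** from the first day of treatment to "disease progression or death from AML, whichever occurs first". Then: "If neither event occurs, PFS will be censored at the date of the last clinical assessment".
- **Section 9.5:** "PFS will be defined as the time from the date of enrollment to disease progression or death from AML whichever occurs first". Then: "If neither event occurs, PFS will be censored at the date of the last assessment".

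No text says which definition governs if they differ.

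**The concern.** The three texts that state the endpoint (synopsis endpoints, 8.3, 9.3.2) agree on death from any cause and on treatment start. The two texts that describe the analysis (synopsis analysis, 9.5) restrict death to AML, and 9.5 also moves the start to enrollment. An analyst programs from the analysis text. Following 9.5 would therefore produce a PFS curve that is not the endpoint the protocol lists. The synopsis contradicts itself, and so does section 9.

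The AML-only wording cannot be read as harmless shorthand, because the censoring sentence that follows it settles the matter. A patient who dies of infection without documented progression has had neither event and is censored. Section 8.3 counts the same patient as an event on the date of death.

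Such deaths are plausible here. Section 2.3 lists sepsis, respiratory failure and multiple organ dysfunction among the frequent serious reactions to venetoclax with azacitidine. The protocol gives no rule for deciding when a death is from AML, so in an open-label study the endpoint would rest on an undefined judgement. If the conflict remains at analysis, the definition could be chosen after the data are seen.

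**Working it through.** The documents give no PFS median, event count, power or target, so there is no stated figure to reproduce. The check is a comparison of the texts, followed by an illustration of size.

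**1. The five definitions**

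| Text | Start | Death counted | Rule for subsequent therapy |
|---|---|---|---|
| Synopsis endpoints | treatment | any cause | none stated |
| Synopsis analysis | treatment | AML only | none stated |
| 8.3 | treatment | any cause | censor at last evaluable assessment before it |
| 9.3.2 | treatment | any cause | none stated |
| 9.5 | enrollment | AML only | none stated |

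**2. Cause of death, against the listed endpoint (synopsis endpoints, 9.3.2)**

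Let f be the share of first events that are non-AML deaths. It is not in the documents. With a constant total hazard λ, censoring those deaths leaves hazard λ(1 − f). The median ln 2/λ becomes ln 2/[λ(1 − f)], so it is multiplied by 1/(1 − f). At the true median the curve reads 0.5^(1 − f) instead of 0.50.

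| Assumed f | Multiplier 1/(1 − f) | Assumed true median of 6.0 months reads | Curve at the true median |
|---|---|---|---|
| 5% | 1/0.95 = 1.05 | 6.3 | 0.518 |
| 10% | 1/0.90 = 1.11 | 6.7 | 0.536 |
| 20% | 1/0.80 = 1.25 | 7.5 | 0.574 |

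The upward direction does not depend on constant hazards: removing one cause from the hazard cannot lower the underlying curve. The formula censors on the date of death, whereas the texts censor at the last assessment. A simulation of 2,000,000 patients with assessments every 28 days and a 6-month median gives nearly the same multipliers: 1.05, 1.11 and 1.24.

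**3. Size against sampling noise**

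Expansion cohorts 2 and 5 have 33 patients each at full size (9.1). In 6,000 simulated cohorts of 33 with a true median of 6 months, 95% of any-cause median estimates lay between about 3.6 and 9.3 months. The AML-only median was the higher of the two in 51, 76 and 96% of runs for f = 5, 10 and 20%. The shift is smaller than the noise, but it is systematic.

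**4. Time zero**

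Screening takes place within 28 days before treatment, with a window of ±3 days (Study Calendar, footnote a). Enrollment precedes first dose, so starting there can only lengthen PFS. The bound is 28/30.44 = 0.92 month, or 31/30.44 = 1.02 months with the window. The actual shift is probably smaller, because registration follows completed pre-study evaluations (4.7) and enrollment rests on the TP53 result (8.6). The enrollment date itself is not defined, and 7.2.1 calls the 28 days approximate.

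**5. Section 9.5 against 8.3**

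These two also differ on subsequent therapy. Section 8.3 drops events after a switch to new therapy; 9.5 would count them. Take an assumed any-cause median of 6 months. Let an assumed share g of patients start new therapy in the second half of the time to their event, with censoring at the previous 28-day assessment. Simulated medians in months, leaving the time-zero difference out:

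| f | g | 9.5 rule | 8.3 rule |
|---|---|---|---|
| 5% | 20% | 6.3 | 7.2 |
| 10% | 20% | 6.6 | 7.2 |
| 20% | 10% | 7.4 | 6.5 |

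The order reverses within plausible values, and neither f nor g is in the documents.

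**The case against.** The strongest reply is that the intended endpoint can be recovered. Both endpoint lists and the dedicated PFS section agree on any-cause death and treatment start. PFS is descriptive, with no test or target, and every death still appears in overall survival (OS). If f is near zero the numbers barely move; at f = 5% the two medians coincide in about half of simulated cohorts of 33. All of this stands, and it limits the severity. It does not remove the conflict, because the wording that departs from the endpoint is in the texts an analyst would implement.

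Several stronger readings are tempting, and the documents do not support them.

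- **That 9.5 flatters PFS compared with 8.3.** The upward direction holds only for cause of death and time zero, measured against the endpoint in the synopsis list and 9.3.2. Against 8.3 the subsequent-therapy rule can work the other way, so the net sign is unknown.
- **That 8.2.5 contradicts 8.3 on transplant.** The treatment-policy statement in 8.2.5 covers OS and relapse from response, not PFS. What remains is an open question: whether transplant counts as subsequent therapy under 8.3.
- **That relapse is left out of duration of response.** Section 9.5 omits it from the event wording but names it in the censoring sentence that follows. The synopsis names it in the event definition. This is loose editing, and it has no bearing on PFS.

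**Conclusion.** The inconsistency is real and should be fixed, with limited impact. As written, 9.5 and the synopsis analysis censor non-AML deaths that the listed endpoint counts, and 9.5 starts the clock earlier than the other four definitions. Against the listed endpoint both departures favour a longer PFS. The first multiplies the median by 1.05 to 1.25 for f between 5 and 20%, assuming constant hazards and an f that the documents do not supply and that could be near zero. The second adds about one month at most. No direction can be claimed for 9.5 against 8.3.

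The primary endpoints, the sample size and the Simon two-stage rule do not use PFS and are unaffected. The textual conflict is certain; its numerical effect in this trial is not.

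**What to change.** 1. In 9.5 and the synopsis analysis, define PFS as the time from first dose of study treatment to the earlier of disease progression or death from any cause, matching the synopsis endpoint list, 8.3 and 9.3.2.
2. Apply one subsequent-therapy rule in the synopsis analysis, 8.3 and 9.5: either carry the 8.3 rule into the other two or remove it from 8.3. State whether stem cell transplant counts as subsequent therapy. Describe the censoring date in the same words in all three.
3. State the analysis set for PFS, because patients enrolled but never dosed have no first-dose date.

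The cost is mainly wording, since deaths are already followed (7.4). If the subsequent-therapy rule is kept, confirm that the start date of new therapy is collected. Counting all deaths from first dose makes reported PFS slightly less favourable than the current 9.5 wording would; the effect of the subsequent-therapy choice has no known sign.

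A separate inconsistency can be settled in the same edit: OS starts at enrollment in 8.2.4 and 9.5, but at treatment start in both synopsis texts and 9.3.2.

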9.6 Pharmacokinetic Analysis

The pharmacokinetics of APR-246 and venetoclax will be summarized using descriptive statistics (mean, standard deviation, CV% mean, geometric mean, CV% geometric mean) and compared with historical control data.

APR-246 and venetoclax concentrations will be determined, and PK parameters (C_{max} , T_{max} , AUC, V_d and CL) will be derived using population pharmacokinetic or non-compartmental methods.

APR-246 concentrations will be determined by a validated high-performance liquid chromatography (HPLC) tandem mass spectrometry (LC/MS/MS) method. A population PK model will be used to estimate PK parameters C_{max} , AUC and CL for each individual patient. APR-246 AUC and C_{max} will then be tested for association with signs of efficacy and safety in the presence of venetoclax. If an observable trend exists, a PK/PD model will be developed to evaluate the exposure-response relationship between APR-246 plasma exposure and outcome measures. Demographic and clinical data (ethnicity, current age, body weight, sex, disease status, etc.) will be utilized to assess interpatient variability in the PK and PK/PD relationships.

APR-246 PK parameters will be compared to historical controls for the assessment of drug-drug interactions.

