
  
 Cohort	Disease	Study Treatment	Prior Therapy Permitted	
 
 			VEN	HMA	LDAC	APR-246	SCT	IC	
   
 Safety Lead-In Cohorts	
 
 Cohort 1	F/L AML	APR-246 + VEN	no	≥1 prior for MDS required	no	no	yes for MDS	no	
 
 Cohort 2	F/L AML	APR-246 + VEN + AZA	no	no	no	no	no	no	
 
 Expansion Cohorts	
 
 Cohort 1	F/L AML	APR-246 + VEN	no	yes for MDS	no	no	yes for MDS	no	
 
 Cohort 2	F/L AML	APR-246 + VEN + AZA	no	no	no	no	no	no	
 
 Cohort 3	R/R AML	APR-246 + VEN	yes	yes	yes	yes for MDS	yes	yes	
 
 Cohort 4	R/R AML	APR-246 + VEN + AZA	yes	no	no	yes for MDS	yes	≤1 prior	
 
 Cohort 5	F/L AML	APR-246 + AZA	no	no	no	no	no	no	
  
								Cohort	Disease	Study Treatment	Prior Therapy Permitted									VEN	HMA	LDAC	APR-246	SCT	IC	Safety Lead-In Cohorts									Cohort 1	F/L AML	APR-246 + VEN	no	≥1 prior for MDS required	no	no	yes for MDS	no	Cohort 2	F/L AML	APR-246 + VEN + AZA	no	no	no	no	no	no	Expansion Cohorts									Cohort 1	F/L AML	APR-246 + VEN	no	yes for MDS	no	no	yes for MDS	no	Cohort 2	F/L AML	APR-246 + VEN + AZA	no	no	no	no	no	no	Cohort 3	R/R AML	APR-246 + VEN	yes	yes	yes	yes for MDS	yes	yes	Cohort 4	R/R AML	APR-246 + VEN + AZA	yes	no	no	yes for MDS	yes	≤1 prior	Cohort 5	F/L AML	APR-246 + AZA	no	no	no	no	no	no
Cohort	Disease	Study Treatment	Prior Therapy Permitted																																																																																																							
			VEN	HMA	LDAC	APR-246	SCT	IC																																																																																																		

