2.4 Azacitidine

Azacitidine is a nucleoside metabolic inhibitor indicated by the U.S. FDA for the treatment of patients with the following French-American-British (FAB) MDS subtypes: refractory anemia (RA) or refractory anemia with ringed sideroblasts (if accompanied by neutropenia or thrombocytopenia or requiring transfusions), refractory anemia with excess blasts (RAEB), refractory anemia with excess blasts in transformation (RAEB-T), and chronic myelomonocytic leukemia (CMML).

In 2008, azacitidine was approved by the European Medicines Agency (EMA) for the treatment of AML patients with 20–30% bone marrow blasts, older than 64 years and who are ineligible for HSCT. EMA approval of azacitidine was expanded on 30 October 2015 to include AML patients with >30% bone marrow blasts.

The recommended starting dose for the first treatment cycle, for all patients regardless of baseline hematology laboratory values, is 75 mg/m² subcutaneously or intravenously, daily for 7 days. Cycles should be repeated every 28 days. Treatment may be continued as long as the patient derives clinical benefit.

Azacitidine is rapidly absorbed after subcutaneous or IV administration with a V_d of 76 ± 26 L and a half-life of 41 ± 8 minutes. C_{max} is reached after about 30 minutes. Azacitidine and its metabolites are known to be substantially excreted by the kidney, and the risk of adverse reactions to this drug may be greater in patients with impaired renal function. Urinary excretion is the primary route of elimination; the cumulated urinary excretion is 85% of radioactive dose with less than 1% recovered in feces over 3 days.

Azacitidine undergoes spontaneous hydrolysis in aqueous solution and is deaminated by cytidine deamidases, whereas APR-246 is glucuronidated. Drug-drug interaction is not likely although both compounds and their degradation products and metabolites are primarily eliminated by urinary excretion. The pharmacokinetic interaction between APR-246 and azacitidine will be investigated in an ongoing parallel trial.

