6.4 Concomitant Treatment

Patients must not receive any other concurrent anti-cancer therapy, including investigational agents while on study treatment. Please also see Section 2.3, regarding known drug-drug interactions for venetoclax, and the importance of avoiding certain food such as grapefruits. This is important both for patient safety and for enabling a correct assessment of an unlikely drug-drug interaction between the study drug APR-246 and venetoclax. For patients concomitantly treated with strong or moderate CYP3A inhibitors, or P-gp inhibitors, the dose of venetoclax should be determined based on institutional practice and current prescribing information. Strong or moderate CYP3A inducers should be avoided (see [APPENDIX VIII](#)).

Patients may continue their baseline medication(s) as long as they are not prohibited. Palliative and supportive care (e.g., anti-emetics, bisphosphonates) for disease-related symptoms will be offered to all patients in the study per institutional practices. AEs will be treated as clinically indicated. All concomitant medications that are currently in use or that become necessary during the study should be recorded.

If the patient develops an acute infusion reaction (\geq Grade 2), the infusion must be stopped until the reaction is resolved to \leq Grade 1. Premedication (e.g., systemic corticosteroids) may be used after the first cycle.

Use of myeloid growth factors is allowed at the discretion of the investigator per institutional practices. If patients experience prolonged myelosuppression, they should be placed on infection prophylaxis per standard of care.

Hydroxyurea may be used for control of leukocytosis.

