8.4 Pharmacokinetics

Plasma concentrations of APR-246 will be measured in Cycle 1, at the timepoints provided in [Table 9](#). Please refer to sections [2.3](#) and [6.4](#), regarding the risk of certain drugs and foods influencing the PK of venetoclax such as grapefruits (see [APPENDIX VII](#)). This is important both for patient safety and for enabling a correct assessment of an unlikely drug-drug interaction between the study drug APR-246 and venetoclax from PK samples.

Table 9. PK Blood Sampling Timepoints for APR-246

APR-246 plasma collection timepoints ^a	Cycle 1			Subsequent Cycles
	D1	D2	D4	D4
Prior to APR-246 infusion	×	×	×	×
At the end of APR-246 infusion	×		×	×
1 hour after the end of APR-246 infusion	×		×	× ^c
3 hours after the end of APR-246 infusion ^b	×			

^a A window of ±15 min applies to each time point.

^b Samples are collected as part of the venetoclax PK sampling scheme below ([Table 10](#)). A single PK sample should be drawn and split into 2 samples for analysis of both drugs at these timepoints.

^c Sample collected between 1 and 3 hours after the end of infusion.

Only in cohorts with venetoclax, plasma concentrations of venetoclax will be measured in Cycle 1, at the timepoints provided in [Table 10](#), and then prior to venetoclax administration on Day 4 of Cycles 2 – 5 ([Table 11](#)).

Table 10. PK Blood Sampling Timepoints for Venetoclax in Cycle 1

Venetoclax plasma collection timepoints	D1	D2	D22	D23
Prior to venetoclax administration ^a	×	×	×	×
2 hours following venetoclax administration ^b	×		×	
3 hours following venetoclax administration ^c	×		×	
4 hours following venetoclax administration ^d	×		×	

6 hours following venetoclax administration ^e	×		×	
8 hours following venetoclax administration ^f	×		×	

^a Baseline sample collected prior to venetoclax administration. On Day 1, it is recommended that venetoclax is given 1 hour after the start of APR-246 infusion (± 10 min), following a meal that will start approximately 15 minutes after initiation of APR-246 infusion. On Day 1, the baseline sample prior to APR-246 infusion can be split into two samples and used as pre-dose sample for venetoclax as well.

^b 3 hours following initiation of APR-246 infusion on Day 1 (± 15 min)

^c 4 hours following initiation of APR-246 infusion on Day 1 (± 15 min)

^d 5 hours following initiation of APR-246 infusion on Day 1 (± 15 min)

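### Section 9.6 assesses interactions on APR-246 only against historical controls, although expansion Cohorts 2 and 5 allow a within-trial (non-randomised) estimate of venetoclax's effect on APR-246

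*Combined protocol and SAP*

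**What the plan says.** Section 9.6 summarises APR-246 and venetoclax PK descriptively, "compared with historical control data", and closes with the sentence that "APR-246 PK parameters will be compared to historical controls for the assessment of drug-drug interactions". The Statistics part of the synopsis names the same comparator. Section 9.6 also plans a population PK model giving individual Cmax, AUC and CL. The covariates it lists are demographic and clinical; venetoclax co-treatment is not among them. No section plans a PK comparison between cohorts.

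Sections 6.4 and 8.4 give the interaction as one reason for the food and drug restrictions. Section 8.4 speaks of "enabling a correct assessment of an unlikely drug-drug interaction between the study drug APR-246 and venetoclax from PK samples". For azacitidine, Section 2.4 says: "The pharmacokinetic interaction between APR-246 and azacitidine will be investigated in an ongoing parallel trial".

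In Table 3, expansion Cohorts 2 and 5 are both front-line AML with every prior-therapy column marked no. Cohort 2 receives APR-246, venetoclax and azacitidine; Cohort 5 receives APR-246 and azacitidine. Table 9 samples APR-246 on Days 1, 2 and 4 of Cycle 1 and on Day 4 of subsequent cycles, with no cohort limit. Section 8.4 does limit venetoclax sampling to the venetoclax cohorts. Of the 3-hour post-infusion APR-246 sample, Table 9 footnote b says: "Samples are collected as part of the venetoclax PK sampling scheme below".

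**The concern.** A difference from historical APR-246 data, or the lack of one, mixes any venetoclax effect with whatever else differs between the data sets. Renal function is one candidate. Section 6.3.7 says moderate impairment can raise APR-246 levels by about 30%, the eligibility criteria admit patients with creatinine clearance above 30 mL/min, and Section 9.6 names no renal adjustment. Azacitidine is another: its interaction with APR-246 is left to another trial, so a historical data set without azacitidine could not separate the two co-medications. The Cohort 2 versus Cohort 5 contrast holds azacitidine, planned dose, sampling scheme and the named assay constant. Unless it is written down, the trial could collect the data and still report only the less specific comparison.

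**Working it through.** **1. Do the two cohorts match?**

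| Feature | Cohort 2 | Cohort 5 | Source |
|---|---|---|---|
| Disease | front-line AML | front-line AML | Table 3 |
| Prior VEN, HMA, LDAC, APR-246, SCT, IC | none | none | Table 3 |
| APR-246 | 4.5 g fixed, Days 1–4 | same | 6.1.1 |
| Azacitidine | 75 mg/m², Days 1–7 | same | 6.1.3 |
| Venetoclax | yes | no | Table 3 |
| APR-246 samples | Table 9 | Table 9 | 8.4 |
| APR-246 assay | one LC/MS/MS method | same | 9.6 |

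**2. How many patients?** Section 9.1 gives a Simon minimax design for each of these cohorts: null rate 20%, target 40%, alpha 0.05, power 80%; 18 patients, continue if more than 4 respond, then 15 more; success at 11 or more of 33. An exact binomial calculation gives alpha 0.0458 and power 0.801, and a search returns this design as minimax. The plan's figure reproduces. A cohort that completes stage 1 therefore has 18 or 33 patients. Two full cohorts use 2 × 33 = 66 of the approximately 70 expansion patients, so 33 in both is a best case if other cohorts enrol.

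**3. How precise is the contrast?** The documents give no between-patient CV, so 30% to 50% is an assumption. For log-normal exposure:

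- SD of log exposure: s = √ln(1 + CV²), which is 0.2936, 0.3853 and 0.4724 at CV 30%, 40% and 50%.
- 90% CI factor with n per cohort: exp[t(0.95, 2n − 2) × s × √(2/n)].
- CV 30%, n = 33: exp(1.669 × 0.2936 × 0.2462) = exp(0.1206) = 1.13.
- CV 50%, n = 18: exp(1.691 × 0.4724 × 0.3333) = exp(0.2663) = 1.31.

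| n per cohort | CV 30% | CV 40% | CV 50% |
|---|---|---|---|
| 33: factor (power at ratio 1.30) | 1.13 (95%) | 1.17 (78%) | 1.21 (60%) |
| 18: factor (power at ratio 1.30) | 1.18 (74%) | 1.24 (51%) | 1.31 (37%) |
| 10: factor (power at ratio 1.30) | 1.26 (47%) | 1.35 (30%) | 1.44 (22%) |

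Power is for a two-sided 5% test. The ratio of 1.30 is illustrative and is taken from the roughly 30% rise in Section 6.3.7. The row for 10 shows the effect of missing later-cycle samples. If the true ratio is 1, the expected interval excludes 1.30 at 18 or 33 per cohort, except at CV 50% with 18, where it just misses (1.305).

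**4. Which samples carry the information?** Without an antifungal, Section 6.1.2 gives venetoclax 100, 200 and 400 mg on Days 1, 2 and 3 of Cycle 1 and 400 mg from Day 4. Section 2.3 gives a half-life of about 26 hours. As a rough guide, assuming simple exponential decline and ignoring absorption, the fraction left after 24 hours is f = 2^(−24/26) = 0.527.

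- Cycle 1 Day 1: no venetoclax is carried over, and 100 mg is taken about one hour into the infusion.
- Cycle 1 Day 4, before that day's dose: 400f + 200f² + 100f³ = 211 + 56 + 15 = 281 mg-equivalents. Steady state at 400 mg is 400f/(1 − f) = 446. The ratio is 0.63.
- Cycle 2 onward, Day 4: at steady state with continuous dosing. If venetoclax was paused late in the previous cycle, as Section 4.1 allows, three daily doses still reach 1 − f³ = 0.85 of steady state.

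Day 1 has the fullest APR-246 profile in Table 9 but the least venetoclax. A Day 1 contrast would lean towards no interaction. Day 4 has three samples (pre-infusion, end of infusion, one afterwards), which suits a population model better than non-compartmental AUC.

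**The case against.** **The contrast is neither randomised nor shown to be concurrent.** This stands. A reader might infer that Cohort 5 is a concurrent control that isolates venetoclax. The documents give no allocation rule and no enrolment timing for the two cohorts, and identical permitted prior therapy does not make the patients identical. Up to five cohorts are planned, so Cohort 5 may not open.

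**The historical data may be adequate.** A reader might infer that they differ in population, renal function, infusion schedule or assay. The documents do not identify the data set, and the sections on earlier studies are largely redacted. Such differences are possible, not shown. This is why the historical comparison should stay.

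**Interaction is a minor question here.** The secondary objective is the PK profile, interaction is not an endpoint, and the plan calls a venetoclax interaction unlikely. This stands against making the within-trial contrast the primary PK analysis. It does not stand against pre-specifying it, since Section 9.6 already commits to an interaction assessment.

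**The plan does not rule the contrast out.** Section 9.0 presents data by treatment arm, and the covariate list in 9.6 is open-ended. Both are true, but neither commits the sponsor to an estimate with a confidence interval.

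**Does Cohort 5 lose the 3-hour sample?** A reader might infer so from footnote b. Table 9 marks that sample without a cohort limit, and the APR-246 sampling item in Section 7.2.2.1 carries no venetoclax-only tag, although the venetoclax item beside it does. Footnote b reads as an instruction to share one draw. It needs clearer wording only.

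**Conclusion.** The concern holds as an omission. The plan's only named comparator for interactions on APR-246 is historical, while the trial's own cohorts can supply an estimate of venetoclax's effect that keeps azacitidine, planned dose, sampling and assay the same. The 90% CI factor is about 1.13 to 1.31, given 18 to 33 patients per cohort with usable samples and an assumed CV of 30% to 50%; at 10 per cohort it is about 1.26 to 1.44. Power at a ratio of 1.30 runs from 95% down to 37% over the main range, so the result should be read as an estimate.

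The documents do not support saying that the historical comparison is invalid, that Cohort 5 is a proper control group, or that an interaction is likely to be missed. The contrast also says nothing about APR-246's effect on venetoclax, because no cohort receives venetoclax without APR-246.

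**What to change.** In Section 9.6 and the synopsis, keep the historical comparison and add a pre-specified Cohort 2 versus Cohort 5 estimate:

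- **Method.** Preferably, venetoclax co-treatment as a covariate on APR-246 CL in the planned population PK model, adjusted for creatinine clearance and body weight. Otherwise, the geometric mean ratio of dose-normalised exposure with a 90% CI. Dose-normalisation is needed because the protocol provides for APR-246 dose reductions.
- **Samples.** Mainly Day 4 of Cycle 2 onward, with Cycle 1 Day 4 as supportive. Cycle 1 Day 1 should not carry the conclusion.
- **Reporting.** An estimate with its CI and the number of patients contributing, with no claim of a powered test. State that allocation is not randomised, that the effect of APR-246 on venetoclax is not addressed, and that only the historical comparison applies if Cohort 5 does not open.
- **Minor.** Reword Table 9 footnote b to say that the 3-hour APR-246 sample applies to all cohorts, and that drawing it with the venetoclax sample applies only where venetoclax is given.

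The cost is a paragraph in 9.6, one model term or table, and one footnote. No patients are added, and no samples beyond those Table 9 already marks.
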